7.3 ADVERSE EVENTS DEFINITIONS

7.3.1 Adverse Event (AE)

An AE is any untoward medical occurrence in a patient or clinical investigation patient administered a pharmaceutical product which does not necessarily have a causal relationship with this treatment.

An AE can therefore be any unfavorable and unintended sign, (e.g., an abnormal laboratory finding), or a disease temporally associated with the use of a medicinal product, whether or not considered related to the medicinal product.

Illnesses with onset during the study or exacerbations of pre-existing illnesses, including but not limited to clinically significant changes in physical examination findings and abnormal objective tests/procedures findings (e.g., X-ray, electrocardiogram [ECG]) should be recorded. The criteria for determining whether an abnormal objective test finding should be reported as an AE are as follows:

- The test result is associated with clinically significant symptoms, and/or
- The test result leads to a discontinuation from the clinical trial, significant additional concomitant drug treatment or other therapy, and/or
- The test result leads to any of the outcomes included in the definition of a SAE (see definition below), and/or
- The test result is considered to be clinically relevant by the Investigator.

For the purpose of this protocol, disease progression or worsening of the underlying disease should not be reported as AEs. This information will be used only for efficacy assessment.

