7.2 SAFETY AND TOLERABILITY ASSESSMENTS

Safety will be assessed throughout the study through clinical and laboratory safety evaluations. These include medical history at screening, physical examinations, vital sign measurements, saturation of oxygen (SpO₂) by pulse oximetry (or arterial blood gas analyses [PaO₂]), and its respective FiO₂ ([Appendix 7 - Imputation of FiO₂ from oxygen flow values. High-flow oxygen](#)

therapy), triplicate 12-lead ECGs, laboratory tests (haematology, coagulation, and chemistry), clinical AE monitoring, and verification of concomitant treatments.

Patients will be evaluable for safety if they have received any partial or complete treatment administration.

All adverse events (AE) and adverse reactions (ARs), based on clinical signs and symptoms and laboratory measurements, will be measured daily until Day 60 (± 3 days), except treatment-related adverse events, treatment-emergent adverse events of special interest, and SAEs that will be measured daily until resolution or stabilisation to at least Grade 1, or to an acceptable level according to the investigator and the Sponsor of his/her designated representative.

Adverse events will be elicited from the patient (or, when appropriate, from a caregiver, surrogate, or the patient's legally authorised representative) by the study site staff using a non-leading question such as "How are you feeling today?" or "Have you had any health concerns since your last visit?"

The investigator and any designees are responsible for detecting, documenting, and reporting events that meet the definition of an AE or SAE and remain responsible for following up AEs that are serious, considered related to the study treatment or the study, or that caused the patient to discontinue the study treatment (see [Section 7.4.2](#)).

Clinical Signs and Symptoms: AEs, including worsening of baseline signs and symptoms of disease observed by the investigator (preferably by the same physician for a same patient) or reported by patients to study nurses will be recorded and graded according to NCI-CTCAE version 5.0, accessible via internet (http://ctep.cancer.gov/protocolDevelopment/electronic_applications/docs/CTCAE_v5_Quick_Reference_8.5x11.pdf). All events, including those considered not related to the study drugs, must be reported in the eCRF.

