7.3.5 Hospitalisation/Prolongation of Hospitalisation

Any event requiring hospitalisation (or prolongation of hospitalisation) that occurs or worsens during the course of a patient's participation in a clinical study must be reported as a SAE unless exempted from SAE reporting (see [Section 7.4.2](#)). Prolongation of hospitalisation is defined as any extension of an inpatient hospitalisation beyond the stay anticipated/required for the initial admission, as determined by the Investigator or treating physician.

Hospitalisations that do not meet criteria for SAE reporting are:

- a. Reasons described in protocol (e.g., IMP) administration, protocol-required intervention/investigations]. However, events requiring hospitalisations or prolongation of hospitalisation as a result of a complication of therapy administration or clinical trial procedures will be reported as SAEs.
- b. Hospitalisation or prolonged hospitalisation for technical, practical or social reasons, in absence of an AE.
- c. Pre-planned hospitalisations: any pre-planned surgery or procedure must be documented in the source documentation. Only if the pre-planned surgery needs to be performed earlier due to a worsening of the condition, should this event (worsened condition) be reported as a SAE.

Other situation that MUST NOT be considered as hospitalisations is the following:

- d. Planned treatments at sites not associated to a hospital and generally considered as minor surgical procedures (i.e., laser eye surgery, arthroscopy, etc.).

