The “Adverse event form” will be used to report targeted signs and symptoms and medical history in case of any significant change (improvement or worsening) during the study, as well as for events that occur after the first drug infusion or any event related to a study procedure within the study period (according to ICH guidelines).

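### The protocol both excludes and requires the reporting of disease worsening as an adverse event, with no rule on which prevails, so AE and SAE counts are not consistently defined

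*Protocol*

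**What the plan says.** **The exclusion.** The last paragraph of Protocol 7.3.1 states that "disease progression or worsening of the underlying disease should not be reported as AEs", and adds: "This information will be used only for efficacy assessment". It makes no exception for serious or fatal events.

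**The inclusions.**
- Earlier in 7.3.1, the events to be recorded include "Illnesses with onset during the study or exacerbations of pre-existing illnesses".
- Protocol 7.2 requires recording and grading of "AEs, including worsening of baseline signs and symptoms of disease observed by the investigator", and then says: "All events, including those considered not related to the study drugs, must be reported in the eCRF".
- Protocol 7.4.1 uses the AE form for "targeted signs and symptoms and medical history in case of any significant change (improvement or worsening) during the study". The footnotes to the assessment tables in 5.7, 5.8 and 5.9 repeat the rule.
- Protocol 7.3.5 says that an event requiring or prolonging hospitalisation, whether new or worsened during participation, "must be reported as a SAE unless exempted from SAE reporting", with a pointer to 7.4.2. Section 7.4.2 lists no exemption and asks for every SAE whatever its relationship to study drug.
- Protocol 7.3.3 makes the cause of death the SAE term, without exception.
- SAP 11.7 defines a TEAE as an event that is new, or that was present and worsened, after treatment began. It has no progression exclusion.

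**The concern.** In this population most patients have two diseases that can worsen during 60 days of follow-up: COVID-19 and the condition behind the immune deficiency. Whether such worsening is an AE is therefore a central definition for the safety data. The protocol answers it both ways.

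TEAEs, grade 3 or higher TEAEs and SAEs are named safety endpoints (Protocol 3.3.2) and remain in SAP Table 3. After early closure, SAP 6.0 makes safety and descriptive efficacy the content of the abbreviated report, so these tables are a main output. Investigators know the treatment arm, so inconsistent classification could differ by arm as well as by site. While the IDMC was active, one limb of its trigger was a 20% excess in SAEs of grade 3 or higher, and that count depended on the same unresolved definition.

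**Working it through.** The plan states no figure on this point, so the check sets the passages side by side.

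**Step 1: what the exclusion covers.** The phrase in 7.3.1 can be read two ways. On the broad reading it excludes progression of any disease, COVID-19 included. On the narrow reading it excludes only the underlying disease. Section 5.5.1 places the disease causing the immune deficiency in the medical and immunodeficiency history, so *underlying disease* is reasonably clear. *Disease progression* is not defined.

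**Step 2: COVID-19 progresses to respiratory failure and prolongs the stay.**
- 7.3.1, broad reading: not an AE. Narrow reading: reportable.
- 7.2: an AE, recorded and graded.
- 7.4.1 and the footnotes: worsening of targeted signs and symptoms goes on the AE form.
- 7.3.5: an SAE. The exemptions listed there (protocol-driven, practical or social, and pre-planned stays) do not apply.
- SAP 11.7: a TEAE if entered.
- Efficacy data: captured by the WHO scale and by the oxygen, ventilation and ICU endpoints (3.3.1, 3.3.3).

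**Step 3: the underlying disease flares or relapses and the patient is readmitted.**
- 7.3.1, either reading: not an AE.
- The exacerbation sentence in 7.3.1: record it.
- 7.4.1: a significant change in medical history goes on the AE form.
- 7.3.5: an SAE. Item (c) of that section even requires SAE reporting when worsening of a condition brings forward a pre-planned operation.
- SAP 11.7: a TEAE if entered.
- Efficacy data: only modification of, or delay in, therapy for the underlying disease (3.3.3). The readmission endpoint is restricted to COVID-19 or its therapy.

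**Step 4: fatal deterioration.** 7.3.3 enters the cause of death as an SAE term, while 7.3.1 bars a progression term. The death itself is counted under every reading, through all-cause mortality and the deaths endpoint.

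**Step 5: precedence.** No section of the protocol or SAP says which passage governs. That sites may differ is an inference from this gap; the documents do not report that they do.

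**Step 6: size.** The documents give no SAE rates for immunocompromised patients that would convert the conflict into a number of events. The following only shows how the former IDMC trigger would react, under assumed rates. With 20 patients per arm, 20 percentage points is 0.20 × 20 = 4 patients. Assume other SAEs in 20% of each arm and true serious deterioration in a proportion d, equal in both arms. Let f be the fraction of deteriorations reported in an arm. The quantity is P(X_E − X_C ≥ 4), with X_E ~ Bin(20, 0.20 + d·f_E) and X_C ~ Bin(20, 0.20 + d·f_C).

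| Reporting | d = 10% | d = 20% | d = 30% |
|---|---|---|---|
| Neither arm reports | 0.08 | 0.08 | 0.08 |
| Both arms report all | 0.11 | 0.13 | 0.13 |
| Experimental all, control half | 0.19 | 0.31 | 0.44 |
| Experimental half, control all | 0.06 | 0.03 | 0.02 |

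A choice applied equally to both arms moves the trigger little. Only unequal reporting moves it materially, and the documents hold no evidence that reporting was unequal.

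**The case against.** The best defence is that the final paragraph of 7.3.1 is a deliberate protocol-specific carve-out from the general sentence on exacerbations. Keeping progression out of AEs and capturing it as efficacy is a legitimate design. Both points stand, so the tension inside 7.3.1 is its weakest part. They do not explain 7.2, 7.4.1, the three footnotes, the SAE sections or SAP 11.7, none of which refers to a carve-out.

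It also stands that the study closed early, IDMC activity has ended (SAP 8.2) and no formal tests are planned (SAP 6.0). The live effect is on descriptive tables only.

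A reader might infer more than the documents support:
- *Improvements are counted as adverse events.* They reach the AE form, but an improvement is neither new nor worsened, so it does not meet the SAP 11.7 TEAE definition. The problem is one of data cleaning.
- *AESI counts are distorted in the same way.* Respiratory failure and underlying-disease flare are not on the AESI list in 7.2.1.
- *Serious deterioration was hidden from the IDMC.* Its remit covered safety and efficacy trends, deaths were a separate limb of the trigger, and respiratory deterioration is recorded in the efficacy data.
- *The effect equals the trigger margin.* In the earlier COVID-19 study (Protocol 1.2.1.3.1), COVID-19 pneumonia, acute respiratory distress syndrome and acute respiratory failure sum to 6.7% + 8.9% + 4.4% = 20.0%, or 4 of 20 patients. Those are AE rates not restricted to serious or grade 3 events, from a different population, summed as if no patient had two of them. They describe a level in one group, whereas the trigger is a between-arm difference that prompts the Chair to contact the other members.

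**Conclusion.** The contradiction is in the current text and should be corrected. One serious deterioration can be an SAE or not an AE at all, depending on the passage followed, and the plan does not choose. The consequence is confined to TEAE, grade 3 or higher and SAE frequencies and, while it operated, the SAE limb of the IDMC trigger. The primary endpoint is untouched. COVID-19 respiratory deterioration remains visible in the efficacy endpoints. Relapse or flare of the underlying disease does not, except through changes or delays in its therapy.

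No magnitude follows from the documents; the table in the working rests on assumed rates. Differences between sites or arms are possible because the trial is open-label and no rule prevails, but they are not demonstrated.

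**What to change.** Reconcile Protocol 7.2, 7.3.1, 7.3.5, 7.4.1, 7.4.2 and the footnotes to 5.7-5.9 into one rule that:
1. defines disease progression separately for COVID-19 and for the underlying disease;
2. states for each whether worsening is an AE, and how serious and fatal deterioration is reported, consistently with 7.3.3;
3. keeps improvements on the symptom checklist, or states that they are excluded from AE counts.

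Add a progression flag, and in SAP 11.7 tabulate TEAEs and SAEs with and without flagged events, so that the report does not depend on which passage a site followed.

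With recruitment closed, the flag can be derived from the AE records together with the respiratory-support, ICU and readmission dates already collected under 7.1.4. That works better for COVID-19 than for the underlying disease, because 7.1.4 ties readmission to COVID-19. For the underlying disease, the recorded changes in its therapy are the main cross-check. A progression event that a site never entered may not be recoverable, and the report should say so.

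The cost is protocol and SAP wording, a derived flag, one extra set of AE tables, and possibly higher all-cause AE counts in both arms.

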7.3.2 Serious Adverse Event (SAE)

A SAE is any adverse experience occurring at any dose that:

- Results in death (is fatal),
- Is life-threatening,
- Requires or prolongs inpatient hospitalisation,
- Results in persistent or significant disability or incapacity,
- Is a congenital anomaly or birth defect,
- Is medically significant, or
- Is any suspected transmission of an infectious agent via a medicinal product.

Medical and scientific judgment should be exercised in deciding whether expedited reporting is appropriate in other situations, such as an important medical event that may not be immediately life-threatening or result in hospitalisation but may jeopardise the patient or may require intervention to prevent one of the outcomes listed in the above definition.

7.3.3 Death

Death as such is the outcome of a SAE and should not be used as the SAE term itself. The cause of death should be recorded as the SAE term instead. When available, the autopsy report will be provided to the Sponsor.

7.3.4 Life-threatening Event

A life-threatening event is defined as any event in which the patient is at risk of death at the time of the event; it does not refer to an event which hypothetically might have caused death if it were more severe.

7.3.5 Hospitalisation/Prolongation of Hospitalisation

Any event requiring hospitalisation (or prolongation of hospitalisation) that occurs or worsens during the course of a patient's participation in a clinical study must be reported as a SAE unless exempted from SAE reporting (see [Section 7.4.2](#)). Prolongation of hospitalisation is defined as any extension of an inpatient hospitalisation beyond the stay anticipated/required for the initial admission, as determined by the Investigator or treating physician.

Hospitalisations that do not meet criteria for SAE reporting are:

- a. Reasons described in protocol (e.g., IMP) administration, protocol-required intervention/investigations]. However, events requiring hospitalisations or prolongation of hospitalisation as a result of a complication of therapy administration or clinical trial procedures will be reported as SAEs.
- b. Hospitalisation or prolonged hospitalisation for technical, practical or social reasons, in absence of an AE.
- c. Pre-planned hospitalisations: any pre-planned surgery or procedure must be documented in the source documentation. Only if the pre-planned surgery needs to be performed earlier due to a worsening of the condition, should this event (worsened condition) be reported as a SAE.

Other situation that MUST NOT be considered as hospitalisations is the following:

- d. Planned treatments at sites not associated to a hospital and generally considered as minor surgical procedures (i.e., laser eye surgery, arthroscopy, etc.).

7.3.6 Unexpected/Unlisted Adverse Event

An AE is considered unexpected/unlisted when the nature or severity of which is not consistent with the applicable reference safety information. The Sponsor will use the reference safety information table included in the most updated IB for plitidepsin for the evaluation of listedness/expectedness of adverse events.

7.3.7 Adverse Reactions

All untoward and unintended responses to an IMP related to any dose administered. This definition covers also medication errors and uses outside what is foreseen in the protocol, including overdose, lack of efficacy, misuse and abuse of the product.

7.3.8 Serious Adverse Reaction (SAR)

A serious adverse reaction (SAR) is defined as any noxious and unintended response to an IMP related to any dose administered that result in death, is life-threatening, requires inpatient hospitalization or prolongation of existing hospitalization, results in persistent or significant disability or incapacity, or is a congenital anomaly or birth defect. In accordance with ICH-E2A, the definition of an adverse reaction implies a reasonable possibility of a causal relationship between the adverse event and the IMP. An adverse reaction, in contrast to an adverse event, is characterised by the fact that a causal relationship between a medicinal product and an occurrence is suspected. It could also be related to the administration procedure when the procedure is an essential part of the IMP administration.

7.3.9 Suspected Unexpected Serious Adverse Reaction (SUSAR)

Adverse reactions due to medicines administered in a clinical trial that are unexpected and serious.

7.3.10 Adverse Events Related to the Study Drug

An AE is considered related to a study drug/IMP if the Investigator's and/or the Sponsor's assessment of causal relationship to the IMP(s) is "Y (yes)" (see [Section 7.3.10](#)). The Investigator will assess the causal relationship of the IMP(s) to the SAE. The Sponsor will consider related to the study drug(s)/IMP(s) those events for which the Investigator and/or the Sponsor assesses the causal relationship with the IMP(s) as "Uk (unknown)" when it cannot rule out a role of the IMP(s) in the event.

7.3.11 Expedited Reporting

The Sponsor is responsible for the appropriate expedited reporting of suspected unexpected serious adverse reactions (SUSAR), including special situations reports (i.e. overdose, medication error) and events considered of special interest to the Competent Authorities. The Sponsor will also report all SAEs, including those that are associated to special situation reports (overdose, medication error), which are unlisted/unexpected and related to the trial drug (IMP) to the investigators and to the IEC / IRBs according to current legislation unless otherwise required and documented by the IEC / IRBs. A SUSAR that meets the seriousness criteria of life-threatening and/or results in death must be reported within seven (7) calendar days. A SUSAR that is not life-threatening or does not result in death must be submitted to the regulatory authorities within fifteen (15) calendar days. In addition to the regulatory authorities, a SUSAR may also need to be reported to other recipients including ethics committee and investigators. In the case of a SUSAR which was initially considered to be non-fatal or non-life-threatening, but which turns out to be fatal or life-threatening, as soon as possible and in any event not later than 7 days after the Sponsor became aware of the reaction being fatal or life-threatening.

7.3.12 Assessment of Causal Relationship to the Study Drug

The Investigator must provide an assessment of the causal relationship of each SAE to the clinical trial IMP(s) according to the following criteria:

- **Y (yes):** there is a reasonable possibility that the IMP(s) caused the SAE [(serious adverse reaction (SAR)].
- **N (not):** there is no reasonable possibility that the IMP(s) caused the SAE and other causes are more probable.
- **UK (Unknown):** only to be used in special situations where the Investigator has insufficient information (i.e., the patient was not seen at his/her centre and no information was shared with the investigator) if none of the above can be used.

7.4 ADVERSE EVENTS REPORTING PROCEDURES

7.4.1 Reporting of Adverse Events

The Sponsor will collect AEs from ICF signature until Day 60 (± 3 days) or until the date of death, whichever occurs first. All AEs suspected to be related to the study drug/IMP must be followed-up after the time of therapy discontinuation until the event or its sequelae resolve or stabilize at an acceptable level to the Investigator and the Sponsor.

All AEs, including medication errors and uses outside what is foreseen in the protocol, must be recorded in English using medical terminology in the source document and the e-CRF. Whenever possible, the Investigator will record the main diagnosis instead of the signs and symptoms normally included in the diagnoses.

Investigators must assess severity (grade) of the event following the NCI-CTCAE v.5 and assign a relationship to each study drug(s)/IMP(s); and pursue and obtain information adequate both to determine the outcome and to assess whether it meets the criteria for classification as a SAE requiring immediate notification to the Sponsor or its designated representative. The Investigator must provide any relevant information as requested by the Sponsor in addition to that already provided in the e-CRF.

Abnormal laboratory tests occurring during the study should only be recorded in the AE section of the e-CRF if the disorder:

- Is associated with clinically significant symptoms, and/or
- Leads to a discontinuation from the study, significant additional concomitant drug treatment or other therapy, and/or
- Leads to any of the outcomes included in the definition of a SAE.
- The test result is considered to be clinically relevant by the Investigator.

Otherwise laboratory results should be reported in the corresponding section of the e-CRF (e.g. biochemistry, haematology).

Signs and symptoms: all signs and symptoms present since the diagnosis of SARS-CoV-2 infection will be collected, including those related with the underlying disease or other concomitant conditions only if present at the time of ICF signature. A separate focus will be done on targeted COVID-19 signs and symptoms present within the last 24 h prior to screening and listed in [Appendix 10](#). They will be also monitored separately by the research team and collected in a specific form of the CRF.

The “Adverse event form” will be used to report targeted signs and symptoms and medical history in case of any significant change (improvement or worsening) during the study, as well as for events that occur after the first drug infusion or any event related to a study procedure within the study period (according to ICH guidelines).

